**2 If available, upload your applicable literature search:**

Name	Created	Modified Date
------	---------	---------------

There are no items to display

ID: VIEW4E02805A7E400  
Name: v2\_Supporting Literature

## Study Procedures

**If you uploaded a separate research protocol document in the 'Research Protocol' page, cite the applicable section and page numbers from that document in the answer boxes below. (If this study is a collaborative UM/VA study please list each procedure that is being conducted and the locations where it is being conducted.)**

- 1 \* Describe all procedures being performed for research purposes only (these procedures would not be done if individuals were not in the study) and when they are performed, including procedures being performed to monitor subjects for safety or to minimize risks:

15 (N=15) Veterans, who are slated for discharge from the VAMHCS inpatient psychiatric unit, will participate in a pilot study to examine the feasibility and acceptability of Recovery Bridge (a web-based tool) as a transitional discharge intervention designed to decrease inpatient re-admission rates and improve Veteran's hope, recovery orientation, and quality of life. Our research staff will monitor the census of the inpatient unit every day and recruit Veterans as early as possible during their stay. Study staff will approach Veterans to explain the study and allow ample time for questions and evaluation of capacity to provide consent. Those consented will be asked to complete a brief (30-45 min) quantitative, baseline assessment. The two PS working on the project will also be available to meet the Veteran at the hospital during the recruitment and assessment process to help establish and build rapport. The consent meeting and the baseline assessment will be done in person on the inpatient unit. They will be conducted in a private and confidential space.

All enrolled Veterans will participate in the Recovery Bridge intervention which will take place over approximately five, 30-75 minute sessions. The first session will take place in-person on the inpatient unit (with the peer specialist using a government issued laptop to access the web-based program) in a private and confidential space. The remaining sessions will occur either in person, over the VA approved video platform, Microsoft Teams, or over the phone, at the participants' convenience. The web-based Recovery Bridge intervention will include instructions on how to tailor and apply myriad Peer Specialist skills and strategies to the context of working with Veterans transitioning from inpatient psychiatric hospitalization to community living. It will also include tailored instructions for using the tools modules relating to: 1) Daily wellness; 2) managing triggers and early warning signs, and; 3) what to do when things breakdown (including crisis and safety plans developed in concert with licensed independent providers). Veterans will be able to access the intervention with assistance from the peer specialist who will have a government issued laptop. Sessions may be audio or video recorded for fidelity purposes.

Veteran Participants:

Approximately 7 days following the final intervention session, all Veteran participants will complete a 30-45 minute quantitative, post-assessment along with a 30-60 minute qualitative interview regardless of the number of intervention sessions attended in order to understand barriers and facilitators to engaging in the intervention. This final assessment along with the qualitative interview will be done over the phone or via VA approved Video platform, Microsoft Teams.

#### Peer and Non-Veteran Participants:

To assess perceptions of the barriers and facilitators to implementation of the Recovery Bridge intervention, stakeholders [including the PS interventionists, a local recovery coordinator (LRC), PS supervisors, and clinician/administrators who work in both inpatient and outpatient mental health settings] will be enrolled into the study and qualitative interviews will be conducted (30-60 minutes). These interviews will be done over the phone or VA approved video platform, Microsoft teams.

#### All Participants:

All qualitative interviews will be conducted by video meeting, or phone and audio-recorded following IRB/ORD approved informed consent procedures via Microsoft Teams. For the Veterans enrolled in the study, the qualitative guidelines will have already been discussed and agreed to during the informed consent process. For the stakeholders and Peer Specialists who will be interviewed, they will be provided an information sheet relaying all the information of the portion of the study they will take part. They will read and discuss with study staff before agreeing to the interview. Recordings of all interviews will be transcribed verbatim by a VA & IRB approved service (Microsoft Teams) then proofread against the recording (and anonymized in the process) by members of the study team.

An administrative data only control sample will be established to pull matched services data for up to an additional 60 Veterans

2 \* **Describe all procedures already being performed for diagnostic or treatment purposes (if not applicable to the study, enter "N/A"):**  
N/A

3 \* **Describe the duration of an individual participant's participation in the study:**  
Veteran subjects participation will last approximately two months. Peer Support Specialist and interventionist and stakeholder participation (as human subjects to complete a single qualitative interview) will last 30-60 minutes each.

4 \* **Describe the amount of time it will take to complete the entire study:**  
The entire study will be completed within 18 months.

5 \* **Describe any additional participant requirements:**  
N/A

ID: VIEW4E0280585B400  
Name: v2\_Study Procedures

## Sample Size and Data Analysis

**If you uploaded a separate research protocol document in the 'Research Protocol' page, cite the applicable section and page numbers from that document in the answer boxes below.**

1 \* **Provide the rationale and sample size calculations for the proposed target population:**  
Our goal is to collect quantitative and qualitative information on proof of concept through a small scale open pilot trial. We have determined that implementing Recovery Bridge with 15 Veterans and conducting qualitative interviews with all Veteran participants, 2 PS interventionists, and up to five or six key stakeholder will be sufficient to determine feasibility and acceptability. We will also collect administrative data (described in companion protocol HP-00110495-Supplemental Administrative Data Protocol) to create a matched group sample of up to 60 to compare services outcomes. As a open-trial this small pilot is not powered.

2 \* **Provide the plan for data analysis. Include in the description the types of comparisons that are planned (e.g., comparison of means, comparison of proportions, regressions, analysis of variance, etc.), which is the primary comparison/analysis, and how the analyses proposed will relate to the primary purposes of the study:**  
Exploratory Outcomes and Analysis for the Active Sample: The Hope Scale (HS), a twelve-item measure that measures hopefulness (23). Research has found HS scores to be positively associated with goal related activities and coping strategies (24) The WHOQOL-BREF. This brief instrument allows for ratings across 8 quality of life dimension and has strong psychometric properties (25). The Maryland Assessment of Recovery: is a brief self-report measure of recovery orientation and has strong psychometric properties (26). The above scales will be assessed during the inpatient stay (baseline) after the patient has signed consent to participate in the study and after the final session of the Recovery Bridge intervention (follow-up) which will be done over video (Microsoft Teams) or the phone. Exploratory analysis of these measures will primarily be descriptive. Effect sizes (mean change + baseline standard deviation) will be calculated but due to small sample size will have a high standard error, hence will not be used to power a larger study

Exploratory Services Related Outcomes Using Active and Control Sub-Samples.

The active sample (n=15) will be compared to a randomly selected contemporaneous (or near-contemporaneous) group-matched sample (n of up to 60) from administrative data on a couple of post-discharge metrics. The first is the SAIL post-discharge engagement metric of 3 outpatient visits within 30 days (or if flagged for suicide risk, 4 outpatient visits within 30 days). The second metric will be whether the patient is re-admitted to in-patient psychiatric hospitalization within 30 days. Matching will be based on diagnostic grouping, age group, and gender. In addition to descriptive statistics (proportions by group), matched pairs analyses (McNemar's test and matched-pairs OR's with 95% confidence intervals) will be used to compare the active sample to the administrative sample on (1) proportion meeting the post-discharge engagement metric, and (2) proportion with inpatient re-hospitalization within 30 days. These analyses are exploratory given limited power and precision of 95% confidence intervals. All quantitative study data will be password protected and stored in a VA REDCap database

Qualitative Analyses: For qualitative data, we will utilize a rapid analysis summary approach. To begin, we will create a summary template with deductively identified key domains (or topics) of interest. We will iteratively refine the summary template by independently summarizing the first few transcripts and then meeting as a team to discuss the summaries, establish agreement, and revise the template with inductively identified domains. When the template is finalized, each of the remaining transcripts will be summarized by an individual and audited by a second person, with disagreements brought to the larger team for discussion. Data from the summaries will be entered into a matrix to begin analysis and identification of common themes. Utilizing this rapid approach will allow us to quickly and efficiently assess the data for the primary outcome of acceptability.

ID: VIEW4E02806052800  
Name: v2\_Sample Size and Data Analysis

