Specific Aim 1: Integrate the My Recovery Plan tool and existing PS tools and strategies to develop a manualized intervention called Recovery Bridge for use by VA PS working to help Veterans make the transition from acute inpatient psychiatric hospitalization to community living.

Specific Aim 2: Complete an open pilot trial (n=15) to examine the feasibility, fidelity, and acceptability of the Recovery Bridge intervention in relation to well specified benchmarks supporting continued and expanded investigation

Specific Aim 3: As part of the open pilot trial: 1) explore the impact of the intervention on readmission rates (at 30 and 90 days), and connection to outpatient care compared to a control group (n of up to 60) identified from administrative data, and; 2) explore the change in recovery and Quality of Life measures over time in the intervention participants.

2 \* Discuss the research design including but not limited to such issues as: probability of group assignment, potential for subject to be randomized to placebo group, use of control subjects, etc.:  
 This is a feasibility and acceptability pilot study and all Veteran participants will receive the intervention; no human subjects control or placebo group will be used.

3 \* Describe the relevant prior experience and gaps in current knowledge. Describe any relevant preliminary data:  
 More knowledge and evidence is needed regarding the use of peer facilitated interventions that support the transition from inpatient mental health hospitalization to living in the community.

As such the overarching purpose of the current study is to optimize existing materials to develop a manualized transitional discharge intervention called Recovery Bridge. The study will also complete an open trial and collect qualitative interview data from a range of stakeholders to examine preliminary outcomes and inform future research to more broadly disseminate and implement the Recovery Bridge Intervention.

4 \* Provide the scientific or scholarly background, rationale, and significance of the research and how it will add to existing knowledge:

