## Audio or Video Recording/Photographs

You indicated that this study involves audio or video recording/photographing.

1

\* Indicate the type of recording (check all that apply):

Video  
 Audio  
 Still Photo  
 Other

1.1 If Other, specify:

2

\* What is the purpose of the recording? (i.e., for therapeutic purposes, to establish treatment fidelity, or to establish reliability of assessments)

We are recording qualitative interviews to ensure that we are capturing main themes and perspectives. We are also recording all inpatient sessions and other subsequent sessions for treatment fidelity.

3

\* Could the recording be likely to cause discomfort in participants or cause harm if their confidentiality were breached?

Yes  No

4

\* How will individuals' identities be protected?

All electronic files of audio/video recordings will be labeled with a code number. The link between code and participant name is password-protected, stored behind the VA

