(5) Potential loss of privacy (small likelihood, moderate degree of seriousness). Some participants may be concerned that they may be identified as a study participant and/or that others may overhear them sharing information pertinent to the study during assessment procedures or intervention sessions. Research staff are thoroughly training to protect the privacy of research participants. To minimize this risk, we meet with participants in private rooms with closed doors at the VA Maryland Health Care System (VAMHCS), and all designated assessment rooms are equipped with sound machines to minimize the likelihood of other building occupants overhearing participants. If meeting over the phone, study team members will verify that the participant is alone in a quiet room with adequate privacy during study visits. If using telehealth, study team members will "lock" the virtual room in addition to verifying the privacy of the room.

(6) Some participants may feel uncomfortable with being audio or video recorded (small likelihood, low degree of seriousness). Participants will be told that the recording device may be turned off at any time during the research visit if this occurs. There is also a slight risk of a breach of confidentiality regarding the identities of the

participant on the recording. To minimize this risk, research staff will label all digital audio/video recording files using an anonymous study code only. All digital recordings and the file that links participants' identities to their anonymous study code are stored on a secure VA computer network (behind the VA 'firewall'). The network and computer files are password protected and passwords are only known by authorized study team members. All digital files are stored in restricted folders, accessible only to authorized study team members. Electronic research files are backed up regularly.

ID: VIEW4E1B52509F000  
Name: v2\_Research Related Risks

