## Protected Health Information (PHI)

You indicated that HIPAA applies and the study will view, access, share, collect, use, or analyze health information that is individually identifiable.

1 \* Which PHI elements will be used or disclosed in this study? (Check all that apply)

- Name
- Address (if more specific than Zip Code)
- Dates
- Ages over age 89
- Telephone numbers
- Fax numbers
- Email addresses
- Social Security numbers
- Medical record numbers
- Health plan beneficiary numbers
- Account numbers
- Certificate/license numbers
- Vehicle identifiers and serial numbers, including license plate numbers
- Device identifiers and serial numbers
- Web universal resource locators (URLs)
- Internet protocol (IP) address numbers
- Biometric identifiers, including fingerprints and voiceprints
- Full-face photographic images and any comparable images
- Any other unique identifying number, characteristic, or code, unless otherwise permitted by the Privacy Rule for re-identification
- None

2 \* Why is the PHI necessary for this research?

*If SSNs are going to be used, describe the specific use and type of SSN to be used (real, scrambled, last 4 digits).*

The PHI is necessary in order to identify and screen for study eligibility criteria. We collect names, addresses, last four of SSN, and phone numbers to be able to contact participants for all aspects of their participation in the study, and to be able to send them a letter if needed. Veteran dates of birth is collected in order to verify age and identify them in our study database. Each participant in the study is assigned an ID number that will be linked to their name, so identifying number/code has been checked for this purpose.

Voiceprints are collected through our audio recordings and these are used to collect data and for training and supervision of staff. Full-face images may be collected via video recording of sessions. These recordings are used for fidelity purposes only.

We will be accessing the Veteran Participants Safety plan that is entered into their CPRS record as a note. This will be done with the Veteran's knowledge after enrollment. No changes to the safety plan will be made.

3 \* What is the source(s) of the PHI?

We collect this information from Veteran participant's medical records or from the participant during the course of their participation in the study.

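### Does the analysis plan need a separate fidelity, attendance and CSQ-8 analysis to serve Aim 2?

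*Combined protocol and SAP*

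**What the plan says.** Specific Aim 2 (Justification, Objective, & Research Design) is to "examine the feasibility, fidelity, and acceptability of the Recovery Bridge intervention in relation to well specified benchmarks supporting continued and expanded investigation". No benchmark value appears in the document.

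Under Sample Size and Data Analysis, item 1 gives the rationale for 15 Veterans: the pilot with its "interviews with all Veteran participants, 2 PS interventionists, and up to five or six key stakeholder will be sufficient to determine feasibility and acceptability". It also says that the pilot is not powered. Item 2 asks the applicant to state "which is the primary comparison/analysis, and how the analyses proposed will relate to the primary purposes of the study". The answer has three parts:

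- descriptive analysis of the Hope Scale, the WHOQOL-BREF and the Maryland Assessment of Recovery ("The above scales will be assessed during the inpatient stay (baseline" and again at follow-up);
- an exploratory matched comparison on two service metrics;
- a rapid qualitative analysis, which it links to acceptability as the primary outcome.

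The CSQ-8 is listed under Surveys/Questionnaires but is not among the scales in item 2.

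Four sections bear on recording. Study Procedures: "Sessions may be audio or video recorded for fidelity purposes". Audio or Video Recording/Photographs: "We are also recording all inpatient sessions and other subsequent sessions for treatment fidelity". Research Related Risks: "Participants will be told that the recording device may be turned off at any time during the research visit". Protected Health Information, on session video: "These recordings are used for fidelity purposes only". The course is described as about five sessions, the first of them on the inpatient unit.

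**The concern.** A pilot's main product is its feasibility, fidelity and acceptability results, and Aim 2 says that these will support a decision on further investigation. A reader who goes from Aim 2 to item 2 finds an analysis explicitly tied to acceptability and none tied to the other two. The exploratory Aim 3 comparison, by contrast, is specified down to McNemar's test.

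Fidelity looks weakest. No section names a checklist, a rater, a rule for choosing sessions or a summary, and the recording statements seem to differ on which sessions exist to be rated. Possible full-face video of psychiatric inpatients is justified by fidelity alone. If the gap mattered, one team could report fidelity from every session, another from inpatient sessions only, and a third not at all, and each could claim to have followed the plan. Attendance and follow-up completion have no stated denominator, and the CSQ-8 has no stated timing or summary.

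**Working it through.** **No figure to reproduce.** The documents give no alpha, power, effect size, benchmark or precision target, so N = 15 cannot be recomputed. The check is mainly a comparison of passages.

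**Aim 2 against the analysis text.**

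- *Acceptability.* Item 2 names it and gives a full qualitative method: a summary template, a second-person audit, and a matrix leading to themes.
- *Feasibility.* Item 1 names the interviews as part of what suffices for it. Study Procedures interviews every Veteran whatever the attendance, to learn about barriers and facilitators to engagement. Item 2's method applies to those interviews. A qualitative analysis therefore exists, and only a numerical one is unstated.
- *Fidelity.* Item 2 does not mention it. The Lay Summary says that the interviews will examine it. The interview guides are listed as uploaded but were not available for this review, so their domains cannot be judged.

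**The two recording statements.** Inputs: 15 Veterans, with about five sessions taken as 5, one of them stated to be inpatient.

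- Planned sessions: 15 x 5 = 75. Inpatient: 15 x 1 = 15, which is 15/75 = 20%. Later: 75 - 15 = 60.
- Study Procedures permits any number of recordings from 0 to 75.
- The recording section implies the 15 inpatient sessions plus some or all of the other 60, so 15 to 75.
- The overlap is 15 to 75. Recording every session satisfies both statements. The right to switch off can lower the achieved number, but it is an ordinary participant protection and not a third rule.

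The recorded set is also fixed by conduct, so two analysts would receive the same files. They could differ only in which files to rate, and aligning the two sentences would not settle that.

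**Does fidelity use require a statistic?** Resources describes regular supervision of those who deliver the manualized intervention. The PHI section says that audio is used for data collection and for training and supervision of staff. Oversight of delivery is a legitimate fidelity purpose even if no proportion is reported.

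**How much the unstated details could move a result.** The success counts and the 12 completers below are assumptions. Intervals are exact (Clopper-Pearson): lower limit = Beta(0.025; x, n - x + 1), upper limit = Beta(0.975; x + 1, n - x).

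| Example | Estimate | 95% CI |
|---|---|---|
| 12/15 | 80.0% | 51.9% to 95.7% |
| 60/75, ignoring clustering | 80.0% | 69.2% to 88.4% |
| 10/15, all enrolled | 66.7% | 38.4% to 88.2% |
| 10/12, completers only | 83.3% | 51.6% to 97.9% |

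The choice of denominator shifts the last estimate by 83.3 - 66.7 = 16.6 points, but the two intervals overlap heavily. For attendance, 4 sessions is 4/5 = 80% of a five-session course and 4/4 = 100% of a four-session one. A count of sessions attended avoids the question.

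The 95% half-width of a CSQ-8 mean, t(0.975, n - 1)/sqrt(n) in SD units, is 0.55 at n = 15, 0.64 at n = 12 and 0.72 at n = 10. These figures show that a pilot of 15 is imprecise. They do not measure an error in the document, because no fidelity proportion and no threshold is stated.

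**The case for a change.** The strongest case for a change is that these are the pilot's own main outcomes, so its small size is no excuse for leaving them out. The form asks how the analyses relate to the primary purposes, and for fidelity the answer is silent. No separate protocol was uploaded, and the companion protocol is described as covering administrative data, so nothing in the document points to a fidelity analysis elsewhere. A paragraph and a table would cost little.

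Much of this stands. Item 2 does omit fidelity and the CSQ-8, and the recording wording is loose. Three things limit its weight.

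- Attendance and follow-up completion are natural feasibility measures, but no section names them as outcomes. The plan cannot be faulted for giving no denominator to measures that it does not set. The 15 enrolled Veterans are the evident base, and the principal investigator already keeps records of accrual, adherence and data completeness (Monitoring Plan - Individual).
- The CSQ-8 measures satisfaction with a service, so its use after the intervention and a plain descriptive summary are the obvious reading.
- The cheap part of the remedy would only write down what analysts would do anyway. The part that would add information, a rated fidelity score, needs an instrument and rater time that the plan does not describe.

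Interviews could be missed through withdrawal, removal at the continued-consent check, loss of contact or refusal. Their number cannot be predicted, and reporting interviews completed out of 15 is routine.

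**Conclusion.** No change follows. The gap is real but small: two descriptive summaries (fidelity and CSQ-8) go unstated, and two sentences on recording are loosely worded yet compatible. Any recorded set from the 15 inpatient sessions to all 75 planned sessions agrees with both. No rule in the plan produces a wrong estimate, test or decision. Feasibility has an analysis through the interviews, and fidelity has at least an interview route.

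This rests on three assumptions: that analysts will report attendance, completion and the CSQ-8 descriptively with all enrolled Veterans as the base; that the Aim 2 benchmarks are set outside the supplied text, since the aim calls them well specified; and that the fidelity recordings serve oversight of delivery as well as any rating. If the team intended a formal fidelity score with a pass mark, its absence would matter more, but nothing supplied says so.

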## Prospective Data

You indicated that the study involves the collection of prospective data.

1 \* Where is the data being collected from? (Check all that apply)

Medical records  
 Medical images  
 Commercial (for profit) entity  
 Publicly available records  
 Schools  
 Other

1.1 If Other, please specify:

2 \* What data fields will you have access to/collect for the study? For example, name, initials, date of birth, Social Security number, income, demographic information, family units, housing, etc.

Name, address, telephone number, last 4 of SSN, inpatient admission and discharge date and notes, outpatient and inpatient encounters scheduled after hospital discharge, and suicide safety plan

You can also upload a copy of the data fields/variables to be collected for the study:

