## Withdrawal of Participants

**If the questions below are not applicable to the research (i.e., chart review), enter "N/A".**

1 **\* Describe anticipated circumstances under which subjects will be withdrawn from the research without their agreement:**

Participants will be withdrawn without their agreement under the following circumstances:

- 1) They have a serious reaction during the study
- 2) They fail to follow instructions from research staff
- 3) If the PI decides that the study is no longer in the best interest of the participant.

2 **\* Describe procedures for orderly termination:**

We will close the study after the last participant interaction occurs and all data has been collected.

3 **\* Describe procedures that will be followed when subjects withdraw from the research, including partial withdrawal from procedures with continued data collection:**

If a participant decides to withdraw from the research, all data already collected will remain in the database, but no new data will be collected from the participant.

ID: VIEW4E1B52531F800  
Name: v2-Withdrawal of Participants

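### Does the rule that no new data are collected after withdrawal bias the 30-day comparison with the record-based controls?

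*Combined protocol and SAP*

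**What the plan says.** Sample Size and Data Analysis, item 2, sets up the comparison: "The active sample (n=15) will be compared to a randomly selected contemporaneous" sample of up to 60, group-matched on diagnosis, age group and gender. The two outcomes are the SAIL engagement metric (3 outpatient visits in 30 days, or 4 for those flagged for suicide risk) and the "proportion with inpatient re-hospitalization within 30 days". The analysis is proportions by group, McNemar's test and matched-pairs odds ratios with 95% confidence intervals. The section calls these analyses exploratory, and item 1 says the pilot is not powered. Study Procedures, item 1, makes the controls an administrative-data sample only.

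Withdrawal of Participants, item 3, answers a prompt that covers withdrawal "including partial withdrawal from procedures with continued data collection". The answer is that "all data already collected will remain in the database, but no new data will be collected from the participant". Item 1 lists separate grounds on which the investigator may withdraw someone, among them "They fail to follow instructions from research staff" and "If the PI decides that the study is no longer in the best interest of the participant".

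On sources, Prospective Data, item 2, lists "outpatient and inpatient encounters scheduled after hospital discharge" among the fields collected. Protected Health Information, item 3, gives the source as the Veteran's "medical records or from the participant during the course of their participation in the study".

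**The concern.** Veterans consent on the inpatient unit and participate for about two months, so the 30-day window after discharge falls inside participation and a Veteran could withdraw during it. If withdrawal also closes the chart to the study, that Veteran's 30-day outcomes are cut short. A control taken from administrative data cannot withdraw, so any loss falls on one side only.

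Counting a cut-short record as no event would lower both active proportions, which flatters the intervention on readmission and penalises it on engagement. Dropping it would set retained Veterans against fully recorded controls. A confidence interval shows neither effect. The supplied text does not say which course to take, and the withdrawal answer passes over the part of its prompt about continued collection.

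**Working it through.** The plan states no withdrawal rate, 30-day readmission rate or engagement rate, so there is no figure to reproduce. The check has two parts.

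**1. Does the withdrawal rule reach the records?**

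- Withdrawal of Participants, item 3: what stops is new data from the participant. Records are not mentioned.
- Protected Health Information, item 3: medical records and the participant are named as two alternative sources. The phrase about the course of participation attaches most naturally to the second.
- Research Related Risks, risk (4), likewise names participant interviews and medical records separately as sources of research data.
- Specific Aim 3 names 90-day readmission, while Study Procedures, item 3, puts participation at about two months. Since 90 days after discharge lies beyond about 60 days of participation, that outcome implies reading records after contact has ended.
- Study Procedures, item 1: every enrolled Veteran gets the intervention, and all are assessed at the end however many sessions they attended. Participant Selection, item 2, defines enrolment as signing consent. Together these make the 15 the consented Veterans, not the retained ones.

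So a stop on record follow-up is one possible reading, not a stated rule. Reading records to day 30 for all 15 is consistent with the text.

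**2. If record follow-up did stop, how large is the effect?**

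Let n = 15, x = events seen, w = Veterans withdrawn before day 30, and u = those among the w whose outcome was still open. Data already collected are kept, so a Veteran already readmitted, or already at the required number of visits, has a known result on that outcome; hence u ≤ w.

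Range of the active proportion: x/n to (x + u)/n, a width of u/15.

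| u | Width |
|---|---|
| 0 | 0 |
| 1 | 1/15 = 6.7 points |
| 2 | 2/15 = 13.3 points |
| 3 | 3/15 = 20.0 points |

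Readmission, assuming x = 2 and w = u = 2:
- counted as not readmitted: 2/15 = 13.3%
- excluded: 2/13 = 15.4%
- both counted as readmitted: 4/15 = 26.7%

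Engagement, assuming 10 of the 13 followed meet the metric and u = 2:
- counted as not met: 10/15 = 66.7%
- excluded: 10/13 = 76.9%
- both counted as met: 12/15 = 80.0%

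Sampling error for comparison: the exact (Clopper-Pearson) 95% interval for 2/15 is 1.7% to 40.5%, a width of 38.8 points.

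Chance of at least one withdrawal in 15 is 1 − (1 − d)^15. For assumed d of 5%, 10% and 20% it is 54%, 79% and 97%. This counts all withdrawals, not only those that leave an outcome open.

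**The case for a change.** The strongest case for a change is that the asymmetry is structural and costs little to close. Two analysts could follow the same text and report 13.3% or 15.4% for readmission in the example. For any control rate between 13.3% and 26.7%, the direction of the comparison would depend on how the two lost Veterans were treated. At least one withdrawal among 15 is quite likely, and the plan's own caveat covers power and precision, not one-sided loss. A rule chosen after seeing the data is weaker than one written beforehand.

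Part of this stands. The partial-withdrawal prompt is unanswered, and the supplied text has no rule for an outcome still open at withdrawal. Nor does it say what happens to data for Veterans withdrawn by the investigator, or removed because they cannot give continued consent (Informed Consent Process, item 8).

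The rest is weaker. The range in which direction could change rests on assumed counts, and its upper end needs both lost Veterans to have been readmitted. The argument that loss is related to outcome draws on the investigator's grounds in item 1, whereas the no-new-data rule in item 3 concerns Veterans who choose to leave. If a choice to leave coincides with a readmission already on record, that outcome is kept. Changing the consent wording might also mean asking enrolled Veterans again, to settle something that the Veteran consent form or the companion administrative-data protocol (HP-00110495), neither of which was available here, may already settle.

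**Conclusion.** No change follows. This is missing detail that an analyst would fill sensibly: take both 30-day outcomes from records for all 15 consented Veterans, as is done for the controls, and report how many records, if any, are incomplete. That course fits the plan and makes follow-up comparable on the two sides.

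On the less favourable reading the indeterminacy is u/15, or 6.7 points for each Veteran whose outcome was still open. Two such Veterans give 13.3 points, about a third of the 38.8-point width of the interval for 2 of 15. It bears on an exploratory, unpowered comparison and leaves the feasibility and acceptability aims untouched. It is zero if records continue to be read or nobody withdraws before day 30.

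The conclusion rests on reading the bar as applying to data from the participant and not to records. That reading has textual support but is not stated outright. All event and withdrawal counts used here are assumptions.
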